1 INTRODUCTION

This document is a clinical investigation plan (CIP) for the INvesTigation to OptimizE Hemodynamic Management of HeartMate II™ Left VentricuLar Assist DEvice Patients using the CardioMEMS™ Pulmonary ArTerY Pressure Sensor in Advanced Heart Failure (INTELLECT 2-HF) study. This observational post market study is intended to characterize hemodynamic-guided management of patients with an existing left ventricular assist device (LVAD) to protocol specified target ranges and its impact on functional status, quality of life, and readmissions. Data will be collected in patients with a HeartMate™ Left Ventricular Assist System (LVAS) and CardioMEMS HF system. Both devices are FDA approved and will be utilized on label. This clinical investigation is sponsored by Abbott. All parties involved in the conduct of the clinical investigation will be qualified by education, training, and experience to perform their tasks and this training will be documented appropriately.

2 BACKGROUND AND JUSTIFICATION FOR CLINICAL INVESTIGATION

Heart failure (HF) is a progressive condition which affects the heart's ability to pump blood to the body's tissues and organs. Symptoms of HF include fluid retention, dyspnea, and exercise intolerance. When patients advance to NYHA class IIIA and are hospitalized, the CardioMEMS™ HF system is indicated for wireless PA pressure monitoring to guide HF management¹. As the disease progresses to NYHA class IIIB, the HeartMate LVAD becomes an important treatment option for patients ineligible for cardiac transplant or those awaiting transplant. The pump is implanted in parallel with the native heart and is intended to provide long-term hemodynamic support^{2,3}. HeartMate use in advanced HF patients results in increased survival, quality of life, and functional status^{2,4}.

The majority of patients respond well clinically to LVAD support and improve to NYHA class I or II. However, approximately 20% of LVAD patients continue to experience poor functional status with NYHA class III or IV symptoms⁴. LVAD patients with worsening HF or impaired pump performance due to suboptimal hemodynamics are often re-hospitalized. In the ROADMAP study, about 80% of LVAD patients were re-hospitalized within a year after implant, and 10% of readmissions were due to pressure/volume management or worsening HF⁵.

Improved hemodynamic monitoring of LVAD patients may reduce the readmission burden due to HF and volume management. CardioMEMS is an implantable wireless pressure sensor proven to reduce hospital admissions in NYHA class III patients. In the CHAMPION trial, CardioMEMS provided daily monitoring of PA pressure to optimize drug therapy in HF patients, resulting in a 37% reduction of HF related hospitalizations¹. In addition to reduced readmission rates, HF management with CardioMEMS leads to improved quality of life, NYHA class, and six-minute walk distance^{1,6}. In LVAD patients, remote monitoring with CardioMEMS should allow physicians to intervene earlier when hemodynamic deterioration occurs. Appropriate medication or pump speed changes can be made to optimize pulmonary artery pressure and indirectly left ventricular filling pressure which may reduce HF hospital readmissions⁷. Frequent hemodynamic optimization may lead to improved functional status and quality of life, especially for patients who are failing to respond well to LVAD therapy.

Currently, there is limited data from patients with both a CardioMEMS device and LVAD. The purpose of this post market study is to characterize and evaluate hemodynamic-guided management in patients that have per indications received a HeartMate LVAD and a CardioMEMS HF System. Patients will be managed with the goal of achieving a PA diastolic pressure in a target range of 8 to 15 mmHg. This range is slightly higher than the PA diastolic pressure range found in healthy subjects (4 to 12 mmHg)⁸ and allows for volume and pressure changes during the course of the day and avoid hypovolemia. The learnings from this feasibility

This confidential document is the property of Abbott and shall not be reproduced, distributed, disclosed or used without the express written consent of Abbott.

study will be used to develop CardioMEMS-guided treatment strategies to improve clinical outcomes of HeartMate patients with poor functional status and provide meaningful evidence for designing future studies.

3 DEVICE(S) UNDER INVESTIGATION

3.1 IDENTIFICATION AND DESCRIPTION OF THE DEVICES UNDER STUDY

3.1.1 Identification

3.1.1.1 The CardioMEMS™ Heart Failure (HF) System

The CardioMEMS HF System provides pulmonary artery (PA) hemodynamic data used for the monitoring and management of heart failure (HF) patients. The system measures PA pressure which physicians use to initiate or modify heart failure treatment.

The CardioMEMS HF System received CE Mark in 2011 and the current certificate was issued by British Standard Institute (BSI) on May 1, 2014. The system received Food and Drug Administration (FDA) approval on May 28, 2014 for commercial use in the United States. The CardioMEMS HF System is currently indicated for wirelessly measuring and monitoring pulmonary artery (PA) pressure and heart rate in New York Heart Association (NYHA) Class III heart failure patients who have been hospitalized for heart failure in the previous year. The hemodynamic data are used by physicians for heart failure management with the goal of reducing heart failure hospitalizations.

3.1.1.2 The HeartMate™ Left Ventricular Assist System (LVAS)

The HeartMate II LVAS is a set of equipment and materials that together comprise a medical device designed to provide therapeutic benefit to those afflicted with advanced heart failure. In service, the LVAS assumes some or all of the workload of the left ventricle, thereby restoring the patient's systemic perfusion while palliating the underlying pathology. The HeartMate II LVAS received FDA approval on January 20, 2010 and CE Mark approval in November, 2005. The FDA approved HeartMate II™ to provide hemodynamic support in patients with advanced refractory left ventricular heart failure; either for bridge to cardiac transplantation (BTT) or destination therapy (DT).

Table 1 – Identification of Devices under Investigation

Device name	Model/ Part Number	Manufacturer	Region/ Country	Investigational or Market Released
CardioMEMS™ PA Sensor and Delivery Catheter	CM2000	Abbott (formerly St. Jude Medical)	United States	Market Released
CardioMEMS™ Patient Electronics System	CMEMS1000, 1010 or 1100	Abbott	United States	Market Released
CardioMEMS™ Hospital Electronics System	CM3000	Abbott	United States	Market Released
HeartMate II™ LVAS	106015	Abbott	United States.	Market Released
HeartMate 3™ LVAS	106524	Abbott	United States	Upon Market Release indication

HeartMate 3™ is a next generation LVAS currently under investigation in the United States in the MOMENTUM 3 Investigational Device Exemption (IDE) clinical trial and Continued Access Protocol (CAP). The HeartMate 3™ LVAS is intended to provide hemodynamic support in patients with advanced refractory left ventricular heart failure; either for short term support, such as a bridge to cardiac transplantation (BTT) or myocardial recovery, or as long

This confidential document is the property of Abbott and shall not be reproduced, distributed, disclosed or used without the express written consent of Abbott.

term support, such as destination therapy (DT). FDA approval for short term support was received in August 2017. Patients with a HeartMate 3 implant can be considered for enrollment into INTELLECT 2 if they meet one of the following criteria:

- Patients with a commercial HeartMate 3 implant
- Short-term support patients such as BTT patients participating in the MOMENTUM 3 CAP
- BTT patients who have completed two year follow-up in the MOMENTUM 3 IDE trial
- Once FDA approval is granted for long-term support, long-term support patients such as DT patients from MOMENTUM 3 CAP or DT patients with complete two year follow-up from MOMENTUM 3 IDE are allowed to be enrolled

3.1.2 Device Description and Intended Purpose

The market approved devices to be used in this study are listed in the Table 1 above. All devices are commercially approved and market released and will be used per the approved labeling, Instructions for Use and Indications. For details regarding the instructions for use, training, storage and handling, preparation for use, precautions, intended populations, and indications for each product, please see the specific user's manual. For CardioMEMS™, the manuals are located at <http://manuals.sjm.com> and for HeartMate™, manuals can be found at <http://www.thoratec.com/medical-professionals/resource-library/index.aspx>.

3.1.3 Intended Purpose within the Clinical Investigation

This clinical investigation is an observational study intended to characterize the use of the CardioMEMS HF hemodynamic monitoring system in patients with an existing HeartMate LVAS. This study will help develop clinical strategies for managing LVAD patients with the use of a hemodynamic monitor and will inform the design of more definitive studies in this patient population.

4 CLINICAL INVESTIGATION DESIGN

4.1 CLINICAL INVESTIGATION DESIGN

The INTELLECT 2-HF Study is a prospective, non-randomized multicenter, single-arm observational study, which will be conducted at up to 25 U.S. centers, and will enroll up to 100 subjects.

The expected duration of enrollment is approximately 18 months with a six month follow-up period. Patients will exit the study when they complete their six month follow-up visit. The total duration of the clinical investigation is expected to be approximately two years.

Patients will be managed with the goal of achieving a PA diastolic pressure in a target range between 8 and 15 mmHg. Clinician discretion is allowed on how to reach this target range by remotely adjusting diuretic/ vasodilator therapy, or by changing pump speeds at clinic visits. The change implemented, and reason for the change, must be documented in the CRF. If no change is made when the patient is outside the target range, the clinician must document the clinical rationale for not making a change. It is recommended that adjustments to diuretic medications be the first approach unless an alternate approach is clinically more appropriate. Pump speed changes in these patients are expected to be infrequent.

4.2 OBJECTIVES

INTELLECT 2 will gather data from patients with both the CardioMEMS™ HF System and HeartMate™ LVAD. Both devices are commercially approved and will be used, as indicated, per the labeling. The objective of this clinical investigation is to understand the role of hemodynamic monitoring in LVAD patients and:

This confidential document is the property of Abbott and shall not be reproduced, distributed, disclosed or used without the express written consent of Abbott.

- Characterize PA pressure measurements with the CardioMEMS HF System in LVAD patients under different clinical and physiologic conditions
- Characterize the effects of PA pressure on functional status, quality of life, and hospital readmissions of LVAD patients
- Evaluate target ranges for PA pressure and assess the impact of medication and pump speed changes on PA pressures

The results from this study will facilitate the design of future studies in this patient population, leading to the development of clinical strategies for managing LVAD patients using information from an implantable hemodynamic monitor.

4.3 ENDPOINTS

There are ten descriptive endpoints in this clinical investigation.

4.3.1 Descriptive Endpoints

1. Change in Six Minute Hall Walk (6MHW) distance from enrollment to six months
2. Changes in CardioMEMS PA pressure over time
3. Percentage of days PA pressure is in the pre-specified target range
4. Changes in PA pressure before 6MHW test to after 6MHW test
5. Device malfunction (e.g. loss of performance in either device)
6. NYHA classification at baseline and each scheduled follow-up visit
7. Health related quality of life (EQ-5D-5L)
8. All-cause hospitalization rate
9. Heart failure hospitalization rate including emergency department visits, or unscheduled clinic visits for worsening HF, volume management, and/or cardiovascular medication management
10. Change in 6MHWD, NYHA class, health related quality of life, or unscheduled hospitalizations by PA pressure

4.3.2 Additional Descriptive Data Analyses

1. CardioMEMS PA pressure data during LVAD speed ramp test, when done as standard of care
2. CardioMEMS PA pressure data during collection of right heart catheterization (RHC) data, when done as standard of care
3. LVAD speed, power, and estimated flow parameters
4. Heart Failure medications (counts and Total Daily Dosage (TDD))

4.4 STUDY POPULATION

The intended population for this clinical investigation is comprised of advanced heart failure patients over the age of 18 years who have a CardioMEMS device and a HeartMate LVAD.

4.4.1 Inclusion Criteria

To participate in this clinical investigation, the subject must meet all of the following inclusion criteria:

1. Subject has CardioMEMS HF PA Sensor and a commercially-approved HeartMate LVAD (Group A)

OR

This confidential document is the property of Abbott and shall not be reproduced, distributed, disclosed or used without the express written consent of Abbott.

Subject has commercially-approved HeartMate LVAD is experiencing NYHA class III symptoms, and has had a previous HF hospitalization and meets FDA indications for CardioMEMS. The CardioMEMS sensor must be implanted within 72 hours of consent (Group B)

2. Signed an informed consent form and agreed to provide access to patient and device data (including CardioMEMS Merlin.net data)
3. No connectivity or transmission problems with CardioMEMS
4. On HeartMate LVAD support for at least 3 months
5. Age \geq 18 years

4.4.2 Exclusion Criteria

Subjects who meet any of the following exclusion criteria must be excluded from the clinical investigation:

1. Current participation in an investigation that is likely to confound study results or affect study outcome
2. Current participation in the MOMENTUM3 IDE clinical trial and has not completed the two year follow-up for that trial
3. Inability to perform 6MHW test due to conditions other than heart failure (e.g. severe arthritis, orthopedic issues, amputation etc.)

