5.8.3 Hospitalizations

All hospitalizations with the associated reasons will be captured as sites become aware and will be reviewed during the follow-up visit. While hospitalized, the follow-up visit assessments will continue to be performed according to the follow-up schedule. Hospitalizations must be reported to the Sponsor through the EDC system upon discovery of the event or, at the latest, if the hospitalization is unknown to the implanting site (i.e. at another facility), during the next follow-up visit.

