6.1 ANALYSIS OF ENDPOINTS

6.1.1 Descriptive Endpoints

The following endpoints will be analyzed using descriptive statistics. Continuous variables will be summarized using numbers of subjects, mean, standard deviation, median, minimum, and maximum. Categorical variables will be summarized using frequency and percentages. Rate data will be summarized using events per patient-time.

1. Change in Six Minute Hall Walk (6MHW) distance will be summarized as change from baseline and using raw values, at 1, 3, and 6 months.
2. Changes in CardioMEMS™ PA pressure over time will include PA systolic, diastolic and mean pressures; heart rate; and cardiac output (calculated using latest algorithm for CardioMEMS) and will be summarized at baseline, throughout the study, and at 6 months.
3. Percentage of days over 6 months that PA diastolic pressure is between 8 and 15 mmHg will be summarized using the total number of days that pressures were measured as the denominator. The percentage will also be calculated at different points during the study. This endpoint will be used to assess the impact of medication and pump speed changes on PA pressures.
4. Changes in PA pressure before the 6MHW test to after the 6MHW test will be summarized at baseline (Group A only) and at 1, 3, and 6 months for both groups.
5. Device malfunction will include all instances of loss of performance of either device and will be summarized separately by device and type of loss of performance at 1, 3, and 6 months.
6. NYHA classification will be analyzed as a categorical variable and as a continuous variable at baseline, 1, 3, and 6 months. Change from baseline in NYHA will be analyzed similarly.
7. Health related quality of life (EQ-5D-5L) total score and visual analogue scale will be scored using the recommended scoring algorithms and analyzed at baseline, 1, 3, and 6 months. The change from baseline in EQ5D-5L will be analyzed similarly.
8. All-cause hospitalization rate will be summarized over 6 months in units of events per patient-time.
9. Heart failure hospitalization rate including emergency department visits, or unscheduled clinic visits for worsening HF, volume management, and/or cardiovascular medication management will be summarized over 6 months in units of events per patient-time.
10. Change in 6MHWD, NYHA class, EQ-5D-5L, or unscheduled hospitalizations will be analyzed descriptively according to subgroups based on PA diastolic pressure.

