Appendix D: 6 Minute Hall Walk With CardioMEMS Readings Pre and Post Test Protocol

Purpose

The purpose of the 6-Minute Hallway Walk test (6MHWT) is to walk as far as possible for 6-minutes, without running or jogging, as a way of measuring functional status. The subject should be encouraged to walk any distance that they can, no matter how small.

Procedure

A CardioMEMS PA pressure reading will be taken two times: once before the 6 Minute Hall Walk test and immediately after the test is over. Be sure to keep the CardioMEMS hospital unit plugged in and running for the post exercise reading. At baseline, Group B will not have a CardioMEMS PA sensor implanted and thus, will not provide a reading before or immediately following the 6MHWT.

Preparing for the Test

1. Establish a 30-meter (or 100 foot) walking course in an enclosed corridor, preferably free of distractions/debris and close to a wall so that if needed, the Subject may rest against it during the test (note: a treadmill is not an acceptable alternate method for this study). You must use a measuring wheel or measuring tape to mark and establish the course.
2. Mark the course at 3-meter (ten foot) intervals using a method unnoticeable to the Subject.
3. Place noticeable markers at either end of the course to indicate the turnaround points. It is advisable to have chairs at either end in case the subject needs to rest.
4. The distance covered during the preceding walk test will not be revealed to the Subject during the study.
5. A warm up prior to the test should NOT be performed. It is suggested that for accuracy the patient be brought to the starting point in a wheel chair so as not to cause undue fatigue prior to the test.
6. Staff should not walk with or pace the patient during the test.
7. If the patient is significantly symptomatic, please encourage the patient to take as many steps as are possible and measure this distance.

Explaining the Test Procedure to the Subject

1. Clearly explain to the Subject what is required of him/her using the following instructions verbatim:

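### The plan gives no value for a six-minute walk that cannot be started because of heart failure, so by default those subjects leave the change summary in a favourable direction (minor)

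*Combined protocol and SAP*

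**What the plan says.** The first descriptive endpoint in section 4.3.1 is "Change in Six Minute Hall Walk (6MHW) distance from enrollment to six months". Under section 6.1.1, item 1, the "distance will be summarized as change from baseline and using raw values, at 1, 3, and 6 months". The general rule there is: "Continuous variables will be summarized using numbers of subjects, mean, standard deviation, median, minimum, and maximum". Section 6.1.1 has no rule for a walk test that was not done. Item 10 uses the same change again, by PA-pressure subgroup.

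The only walk-related exclusion in section 4.4.2 is "Inability to perform 6MHW test due to conditions other than heart failure (e.g. severe arthritis, orthopedic issues, amputation etc".). HF-related inability is therefore compatible with enrollment. Section 5.13 does not list inability to walk as a ground for withdrawal. Section 5.5.2 requires the test at every scheduled visit, and section 5.8.3 adds: "While hospitalized, the follow-up visit assessments will continue to be performed according to the follow-up schedule".

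Appendix D deals well with poor walkers. "The subject should be encouraged to walk any distance that they can, no matter how small", it says, and further: "If the patient is significantly symptomatic, please encourage the patient to take as many steps as are possible and measure this distance". For a test broken off early, it has the distance reached, the time and the reason recorded. The timer starts at the subject's first step. Nothing is said about a subject who cannot take that step.

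**The concern.** Being unable to start the walk because of HF is the worst result this endpoint can have. If it is left blank, the summary covers only those well enough to walk, and the reason for the blank is the outcome itself. The mean change then looks better than it should.

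The results have planned uses. Section 6 says that any p-values will help pick endpoints for future trials, and that outcomes by PA-pressure subgroup will help find pressure ranges with good clinical results. If subjects too ill to walk fall mainly in one subgroup, the blank flatters that subgroup most.

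The plan already has a convention of this kind for the companion measure. Appendix C assigns NYHA class IV to any inotrope-dependent patient after enrollment. The same deteriorating patient could count as worst on NYHA and be absent from the walk distance.

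**Working it through.** **1. Which subjects are affected.** Setting Appendix D beside section 6.1.1:

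- Walks a few steps: scored (distance measured).
- Starts and stops early: scored (distance, time and reason recorded).
- Under follow-up, cannot start because of HF: no rule. A site could enter 0 m or leave the field blank, and both fit the text. Blank is the likelier default, since no test took place.
- Unable at baseline: no baseline distance, so no computable change.

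**2. Direction.** Let m be the mean change in those who walked, p the share who had a baseline distance but cannot start at month 6, and b their baseline distance.

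Mean with 0 m scored = (1 − p)·m − p·b

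Shift from the walkers-only mean = −p·(m + b)

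No change can be lower than −b, so for any plausible m the shift is downward. Leaving these subjects out is favourable to the result.

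**3. Size.** The documents give no SD, baseline distance, expected change or inability rate, and the sample size of 100 (section 6.2) comes without a calculation, so there is no plan figure to reproduce. All inputs here are assumptions: m = +40 m, b = 200 to 300 m, SD of change 80 to 100 m, 90 subjects assessed, SE = SD/√(90(1 − p)).

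| p | Subjects of 90 | Mean with 0 m scored | Shift p·(40 + b) | SE | Shift/SE |
|---|---|---|---|---|---|
| 2% | 1.8 | 33.2 to 35.2 m | 4.8 to 6.8 m | 8.5 to 10.6 m | 0.5 to 0.8 |
| 5% | 4.5 | 23 to 28 m | 12 to 17 m | 8.7 to 10.8 m | 1.1 to 2.0 |
| 10% | 9 | 6 to 16 m | 24 to 34 m | 8.9 to 11.1 m | 2.2 to 3.8 |

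A second set of assumptions (m = 0 to 30 m, b = 150 to 300 m) gives shifts of 3.0 to 6.6 m at 2%, 7.5 to 16.5 m at 5%, and 15 to 33 m at 10%. For comparison, the 95% half-width with n = 100 is 1.96·SD/√100, or 11.8 to 23.5 m for an SD of 60 to 120 m. At 2% the shift is inside that half-width for every SD.

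**4. Can the documents supply p?** No. Two figures in section 2 look usable but are not.

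- *Readmission.* About 80% readmitted within a year implies a constant hazard of −ln(0.2) = 1.61 per year. With an assumed stay of 5 to 10 days, 1.61 × 5/365 to 1.61 × 10/365 = 2.2% to 4.4% are in hospital on a given day. That covers all causes. Section 2 ties only 10% of readmissions to pressure/volume management or worsening HF; with equal stays that leaves 0.2% to 0.4%, under half a subject in 90. Being in hospital is also not the same as being unable to take a step.
- *NYHA.* About 20% of LVAD patients are in class III or IV. Appendix C describes class III as comfortable at rest with limited activity, and class IV as unable to be active without discomfort. Neither means unable to start a walk.

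**5. Baseline.** A subject unable at baseline who later walks a distance d would have a change of +d if baseline were scored 0 m. Leaving that subject out lowers the reported mean whenever d exceeds m. This is a lost gain, opposite in sign to step 2.

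**The case against.** The strongest reply is that Appendix D is written to keep sick patients in the data. A fall from 300 m to 5 m is recorded and counted, so only the subject who takes no step is lost. This stands, and it sets the limits of the point. A reader might infer that everyone limited by HF has no walk score and that the worst deteriorations in general drop out; Appendix D does not support that. Nor is exclusion criterion 3 itself at fault. It only shows that such subjects can be enrolled.

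Second, no document figure supports a rate of 5% or 10%. This also stands. The visit windows in Table 2 (±7 days at months 1 and 3, ±30 days at month 6) allow many tests to be done outside an admission. In the other direction, inability can occur outside hospital, and the enrolled group may be sicker than the population described in section 2.

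Third, a required test that is missed may be logged as a deviation with its reason (section 8.1), the number of subjects and the median accompany each mean, and severe decline also shows in NYHA class, EQ-5D-5L and hospitalizations. This stands in part. The count shows that values are missing but not why, and a deviation record does not put a value into the summary. The case report forms are not in the documents, so a reason field may already exist.

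Fourth, section 6 describes descriptive endpoints without formal hypothesis tests, and section 6.4 sets no success criterion. This stands and lowers the severity. Some relevance remains, because section 6 uses the results to choose endpoints and pressure ranges for later trials.

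**Conclusion.** The gap is real but narrow. Neither Appendix D nor section 6.1.1, item 1, gives a value when a subject under follow-up cannot start the walk because of HF. By default that subject is missing from the change summary and from endpoint 10, and the mean change is biased in a favourable direction.

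The size is unknown. Under the stated assumptions, 2% affected gives about 5 to 7 m, within sampling error, and it takes about 5% to reach 1 to 2 SE. A reader might take the in-hospital or NYHA III/IV percentages as inability rates and conclude that the bias is large; the documents do not support that. Subjects unable at baseline are a separate issue with the opposite sign.

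Severity is minor: this is a descriptive feasibility study with no success criterion. The conclusion rests on the reading that a test not started would be left blank, which the plan neither states nor rules out.

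**What to change.** In Appendix D and section 6.1.1, item 1, state that a test not started because of HF is recorded as 0 m, including when the subject is in hospital for it, and that any other missed test is recorded as missing with its reason. Report the count of each at every visit. Keep the baseline count on its own line, since it acts in the other direction. Show the 6MHW change with and without the 0 m scores, and do the same in endpoint 10.

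The cost is one sentence in Appendix D with a matching line in section 6.1.1, one reason field on the walk-test form if there is none, and one extra table row. The downside is a slightly less favourable and more skewed mean change; the median is already planned. The reason should be collected at the visit, because it cannot be reliably recovered afterwards. The change does not affect patient management.
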